Adverse events will be reviewed on a weekly basis by three independent cardiologists (Drs. [name], [name] and [name]). Serious adverse events will be reported to the Columbia IRB per institutional guidelines within 24 hours.

7. Who is monitoring the study?

The principal investigator/co-Investigators will collect and manage the data for the entire study. The DSMB will monitor the safety of the study.

8. DSMB Meetings:

The DSMB will meet at 6 month scheduled intervals. They can also meet, at their discretion, in response to any SAE that is reported. At a meeting, the DSMB can request unblinding of the trial and for a statistical analysis of safety events without the PI present. In response to the analysis, they can recommend: continuation of the study without modification, continuation of the study with suggestion, continuation of the study with mandatory changes, suspension of enrollment and termination of study. All recommendations will be part of a DSMB report and will be submitted to the IRB after every meeting.

2. Adams KF, Jr., Fonarow GC, Emerman CL, LeJemtel TH, Costanzo MR, Abraham WT, Berkowitz RL, Galvao M, Horton DP, Committee ASA, Investigators. Characteristics and outcomes of patients hospitalized for heart failure in the United States: rationale, design, and preliminary observations from the first 100,000 cases in the Acute Decompensated Heart Failure National Registry (ADHERE). *Am Heart J.* 2005;149(2):209-16. doi: 10.1016/j.ahj.2004.08.005. PubMed PMID: 15846257.

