- Planned major surgery within the study period
- Female patients who are pregnant, nursing, or of childbearing potential while not practicing effective chemical contraceptive methods (i.e. oral, implanted, injectable, or transdermal contraceptive hormones; intrauterine device)
- Current abuse of alcohol or drugs
- Life-expectancy of less than 1 year due to co-existing morbid illness
- Liver disease with ALT or AST >3 times upper normal limit (it is possible to repeat this measurement once within a month)
- Advanced lung disease such as COPD
- Significant comorbidity or issue that makes the patient unsuitable for participation as judged by the investigator

- Participation in another study involving long-term medical intervention (participation in device studies is allowed)

Randomization: After obtaining informed consent, subjects who meet all the inclusion criteria and none of the exclusion criteria will be randomized. Patients will be randomly assigned in a 1:1 ratio to metformin (1000mg twice a day) or placebo treatment groups. The randomization code will be generated by the Columbia University Irving Institution Biostatistics Epidemiology and Research Design Resource (BERD) and held by the Columbia University Medical Center (CUMC) research pharmacy in opaque envelopes prior to the initiation of patient recruitment to ensure allocation concealment. The study drug will be dispensed by the research pharmacy based on randomization assignment. Principal investigator/Co-investigators are responsible to assess the eligibility criteria. Patients and physicians will be blinded to the intervention allocation. Randomization will be performed in block permutations designed by BERD in order to balance the issue of maintaining similarity between treatment groups while simultaneously not employing block sizes which are so small that it is possible to guess some allocations, thus reducing blinding in the trial. A separate randomization table will be generated for those subjects who agree to the PET sub-study (IRB AAR9360). The goal of having two tables is to maintain balanced enrollment between those that do and do not agree to participate in the PET sub-study.

Study Intervention and Procedures

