The primary outcome in this study will be change in VE/VCO₂ slope. The VO₂ change outcomes will be assessed for normality using standard visual assessments (Q-Q plots and histograms) and statistical tests (Kolmogorov-Smirnov). If VE/VCO₂ slope change demonstrates evidence for non-normality, we will natural log transform values for our primary analyses. Prior to testing for differences, we will compare important clinical, laboratory and demographic characteristics between groups (treatment vs. control) to ensure that randomization achieved between groups balance on these important covariates. For variables that are unbalanced by treatment group (determined via statistically significant difference $p<0.05$), we will include these variables in multivariable models of the primary endpoint as described below. Linear regression models will be used to regress mean weight change on treatment group using intention-to-treat principles. If preliminary descriptive analyses indicate a need for multivariable models (see above), the relevant adjustments will be made to our regression models. Analysis of secondary outcomes will be conducted using contingency tables and Fisher's exact chi-square tests; for these outcomes, we will also utilize a modified Poisson regression model with robust error variance to assess the relative risk (separate regressions for each outcome). This modified Poisson model has been described previously and allows for multivariable models to be constructed should they be deemed necessary. Once a patient is randomized, they will be included in final analyses according to intention-to-treat principles regardless of whether they complete the study protocol. If patients are lost-to-follow up and final outcome assessments cannot be made we will use the "last observation carried forward" approach to assign a final outcome value. Additional sensitivity analyses will be performed by assigning final outcome values assuming patients in the treatment group had 10% lower mean weight loss and patients in the control group had 10% greater mean weight loss. This is very conservative approach that will inform the potential for differential outcomes according to follow-up status to explain our observed findings. However, we expect very little loss-to-follow up as these patients receive regular care at our center and are likely to return to the hospital regardless of continued study participation.

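### Randomisation uses separate tables for PET and non-PET patients, but the primary regression has no term for the table; adding one is a nearly free gain in precision

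*Combined protocol and SAP*

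**What the plan says.** Randomization (Combined protocol and SAP) sets 1:1 allocation and states: "Randomization will be performed in block permutations designed by BERD". Block size is not given. It then adds: "A separate randomization table will be generated for those subjects who agree to the PET sub-study (IRB AAR9360". The reason given is: "The goal of having two tables is to maintain balanced enrollment between those that do and do not agree to participate in the PET sub-study".

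Statistical Approach specifies the primary model: "Linear regression models will be used to regress mean weight change on treatment group using intention-to-treat principles". Before that, "we will compare important clinical, laboratory and demographic characteristics between groups (treatment vs. control"), and the entry rule is: "For variables that are unbalanced by treatment group (determined via statistically significant difference $p<0.05$), we will include these variables in multivariable models". Neither PET agreement nor the randomisation table is named as a model term, as a variable to be screened, or in a sensitivity analysis.

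The PET Sub-study section says that patients are approached for PET when they enrol in the main trial. It gives neither a target number nor a rule for the main comparison.

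**The concern.** Two blocked tables split by PET agreement make that agreement a stratification factor, whatever the reason for having two tables. The analysis should normally carry the factors used in the randomisation. If it does not, any outcome variance between strata stays in the error term, although the design has removed that variance from the treatment contrast. The reported standard error then overstates the true one.

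The covariate rule does not repair this. It admits variables that differ between arms, and within-table blocking is there to stop this one from differing. The route that the plan offers for adjustment therefore works against the factor on which the allocation was built. At stake are some precision and the nominal size of the test, in a trial of 25 per arm with no allowance for dropout in the sample size.

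**Working it through.** **Inputs.** From Power for VE/VCO₂: effect −5, spread 6, 25 per arm, alpha 0.05 (taken as two-sided), stated power 83%. Assumed, because the documents do not say: 20 PET and 30 non-PET patients, balanced arms in each table, block sizes of 4 to 10, and the share R² of the variance in slope change that the stratum explains (0 to 20%).

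**1. The plan's own figure.** SE = 6 × √(2/25) = 1.697, and 5/1.697 = 2.946. Then 2.946 − 1.960 = 0.986, and Φ(0.986) = 83.8%. The noncentral t gives 82.3%. The stated 83% therefore reproduces if the spread of 6 is an SD. Read literally as a variance (SD 2.449), it gives power above 99.9%. SD 6 is used below.

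**2. Can the p<0.05 rule select the stratum?** Every PET-by-arm table possible under within-table blocking was enumerated, with 10, 20 or 25 PET patients out of 50 and an uncorrected chi-square test. The smallest attainable p was 0.36 for blocks of 4, 6 or 8 and 0.16 for blocks of 10. In simulated allocations with blocks of 4, 6 and 8 (1,500 per setting), the rule triggered in 0%. Without stratification it would trigger in about 4%.

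Two illustrations with 20 PET and 30 non-PET patients, with opposite imbalances in the two strata:
- PET 11 v 9, non-PET 14 v 16: Fisher p = 0.77.
- PET 12 v 8, non-PET 13 v 17: Fisher p = 0.39.

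**3. What R² means in slope units.** With 40% in PET and total variance 36, R² = 0.4 × 0.6 × g²/36, so g = √(36 × R²/0.24). R² of 5%, 10% and 20% gives g = √7.5 = 2.7, √15 = 3.9 and √30 = 5.5 units of slope change.

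**4. Standard error and size.** The unadjusted SE is too large by 1/√(1 − R²): 1.026, 1.054 and 1.118. The true size is approximately 2 × [1 − Φ(1.96/√(1 − R²))]: 4.4%, 3.9% and 2.8%.

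**5. Simulated size and power** (total SD 6, true difference 5 for power):

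| R² | Stratum difference g | Size, unadjusted | Power, unadjusted | Power, adjusted |
|---|---|---|---|---|
| 0% | 0 | 5.0% | 82% | 82% |
| 5% | 2.7 | 4.3% | 83% | 84% |
| 10% | 3.9 | 4.0% | 83% | 86% |
| 20% | 5.5 | 2.9% | 85% | 90% |

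Repeat simulations move the sizes by a few tenths of a point. With the stratum in the model, the size stays at about 5% in every row.

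**The case against.** The case against is strong on consequence.

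- **Validity and planned power.** A reader might infer that the primary result would be biased or the trial underpowered. It would not. Omitting a balanced stratum leaves the estimate unbiased and makes the test conservative, never anti-conservative. Unadjusted power stays at 82% to 85% throughout, so what is lost is a possible gain over the plan. This stands.
- **The link to outcome.** A reader might suppose that patients who accept scans are fitter and so respond differently. The documents offer no evidence of this. Any enrolled patient may join the sub-study, all patients do the exercise test, and the endpoint is a change from baseline. At R² = 0 the omission costs nothing. The 20% row needs a 5.5-unit difference between strata, more than the 5 units assumed for the drug. This stands too.
- **Never versus almost never.** It is tempting to say that the rule cannot select the stratum at all. Block size and sub-study size are unstated, and blocks that are very large relative to a stratum would weaken the forced balance. Only almost never is supported.
- **A wasted second table.** The stated aim is balanced enrolment, and balanced arms also serve the sub-study's own comparison. The second table is therefore not wasted if the main model ignores it.
- **Timing of PET agreement.** A reader might see a gap in when agreement is recorded. Choosing between tables already requires the decision before allocation, and the sub-study section places recruitment at enrolment.

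None of this answers the narrower point: the model omits the factor used in the allocation, and the existing adjustment clause will not bring it in.

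**Conclusion.** The point holds as a modest mismatch between randomisation and analysis. It does not threaten validity. The stratum is in the design, absent from the primary model, and practically out of reach of the p<0.05 rule.

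For a stratum explaining up to 10% of the variance, adjustment gains 0 to about 3 power points. At the 20% extreme it gains about 5, and the unadjusted size falls to 2.9%. With no relation to outcome, nothing is gained and essentially nothing is lost.

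These sizes rest on an assumed 20/30 split, an SD of 6 and an R² range that the documents do not inform. The conclusion about the rule rests on blocks that are small relative to the strata. This is a free improvement and not a required correction.

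**What to change.** Under Statistical Approach, state that the primary linear model for change in VE/VCO₂ slope includes the randomisation table used (PET or non-PET) as a fixed covariate, whatever the baseline p-values. Define it as assigned at randomisation, unchanged if the patient later declines the scan.

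Correct the same sentence so that its outcome is the primary endpoint. It now names mean weight change, and adding a covariate without that correction would refine a model for the wrong variable.

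The change need not extend to continuous secondary endpoints on this ground, because the section specifies no linear models for them.

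Cost: a short wording change and one residual degree of freedom (50 − 2 = 48 becomes 47). There are no new data, and N stays at 25 per arm.

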Patients will be randomized to either metformin or placebo. Metformin dose will begin with 500mg twice a day for the first two weeks and then increase to 1000mg twice a day for the remainder of the trial. In order to minimize GI side effects, the medication will be taken with a meal. The intervention will last 180 days. Prior to randomization all potential study subjects will be evaluated with complete medical history and brief physical examination, complete review of home medications, measurement of vital signs and body weight with calibrated scale, serum collection for basic metabolic panel, hemoglobin A1c and liver function test. All patients will also undergo cardiopulmonary exercise testing and transthoracic echocardiography. Patients who meet all the inclusion criteria will be required to complete the informed consent form. Patients will have 2 office visits in total, one at day 1 (baseline) and one on day 180 (final). On day 30, participants will have a blood work for basic metabolic panel, venous lactate and fasting plasma glucose for adverse event assessment (safety). On the final visit, patients will undergo repeat echo, labs and cardiopulmonary exercise testing. The timing of all procedures in this study is outlined in the table 1. Procedural timeline and further details of the relevant procedures are as follows:

Medical history and physical exam: Subjects will be asked to provide information about their basic demographics: age, gender, and race as well as previous and current health and medications. The subject will have his or her height, weight, blood pressure both supine and standing, heart rate, respiratory rate and body temperature recorded. A HF-focused physical examination will be performed and recorded. A Minnesota Living with Heart Failure Questionnaire will be completed.

Blood tests:

Blood be drawn via venipuncture. The following will be prospectively measured for every patient at the indicated time points.

- Screening: fasting insulin and glucose level, basic metabolic, liver function test and HgbA1c
- Baseline: , BNP, venous lactate
- Safety: basic metabolic panel, venous lactate and fasting glucose
- Final: basic metabolic panel, BNP

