Clinical Data Collection: This study will collect all data obtained during routine clinical care of all patients who participate in this study. Retrospective data will be collected. All patients will be followed prospectively until death. Trained research staff will extract data from electronic medical records. We will acquire longitudinal clinical information, including complications, hospitalizations, medication use, laboratory values, echocardiographic data, hemodynamic data, as well as mortality.

Table 1: Procedural Timeline

Day Number	0	30	180	210
Type of Visit	Screening/Baseline	Safety	Final Visit	Safety Follow
Informed Consent	X			
Medical History	X			
Vital Signs	X			
MLHFQ	X		X	
Physical Exam	X		X	
Adverse Event		X	X	X
Pregnancy Test	X		X	
Basic Metabolic Panel	X	X		
Fasting Plasma Glucose	X	X	X	
Fasting Insulin Level	X			
Hepatic Function Panel	X			
BNP	X		X	
Hemoglobin A1c	X		X	

Venous Lactate	X	X	X	
VAS and Likert Scale	X		X	
Echocardiogram	X		X	
Venous Reactivity	X		X	
CPET	X		X	
Study Med Allocation	X			
Biomarker Blood Samples	X		X	
PET Substudy				
13N-Ammonia	X		X	
18F-FDG	X		X	

Primary Endpoint Rationale: The primary endpoint is a change in the slope of the ventilation versus carbon dioxide production (VE/VCO₂). Peak VO₂ has been considered in heart failure literature as a strong predictor for HF outcomes and was the original variable studied in that population. However, a confounder with metformin is that in normal patients without heart failure, metformin treatment has been shown to slightly decrease VO₂(27). The mechanism behind this is possible direct inhibition of complex I of the mitochondrial electron transport system(28). The slope of the relationship between minute ventilation and CO₂ production (VE/VCO₂) has been also thoroughly studied in systolic heart failure as a marker of ventilator efficiency and overall prognosis(29). As demonstrated in over 20 papers (summarized in reference 29) and in the AHA guidelines (26), the VE/VCO₂ slope more powerfully predicts mortality, hospitalization or both than peak VO₂. This has been shown to be a sensitive index of cardiorespiratory fitness in patients taking metformin with insulin resistance and heart failure and is not confounded by any inhibitory interactions between metformin and the variable (30). Thus we have excluded peak VO₂ as a primary endpoint and will instead use VE/VCO₂ as the primary endpoint for power analysis.

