Clinical Events: Subjects will be followed for 180 days following their enrollment and the following ADHF-events will be recorded every three months during office visits or by telephone contact: (i) Unscheduled intravenous diuretic therapy in-office; (ii) Emergency room visit for ADHF; (iii) Hospital admission for ADHF.

Data Management: Study data will be collected and recorded by study personnel under the supervision of the principal investigator. All subjects enrolled in the study will be given a unique identifier, which will be used for all further evaluations. Any information obtained during this study and identified with the patient will remain confidential. All the data will be stored on a mainframe network computer, which can only be retrieved by members of the research team through personalized logon codes. At least quarterly, data analyses regarding accuracy of data entry will be performed by a biostatistical consultant and potential errors will be reported to the principal investigator and study personnel for correction.

Safety Monitoring: A data monitoring committee of three members ([name], Dr.

[name] and [name]) will be established to evaluate safety, with a pre-specified stopping rule for harm but not for efficacy. Renal function, fasting glucose and venous lactate will be assessed at baseline, safety lab (day 30) and final visit (day 90). Safety will be assessed by tracking all adverse events on a weekly basis and serious adverse events within 24 hours of discovery. Serious adverse events for this trial will include death, life threatening illness, disability, congenital abnormality, any hospitalization, hypoglycemia (serum glucose <60g/dL), and new lactic acidosis (lactate >2.0mmol/L) with specific responses to these events as detailed in the Protection of Human Subjects section.

Statistical Approach

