Upon recognition of eligible subjects by the primary cardiologist/heart failure specialist and patients' willingness for participation, the study team will be notified and review the patients' willingness as documented. The investigator will review all the inclusion and exclusion criteria as outlined in the proposal. The principal investigator will obtain an appropriately signed and witnessed informed consent and HIPAA authorization form. All participants in this study, including co-investigators and research staff have been certified in Good Clinical Practices. All subjects will be assigned a unique identification (ID) number by the study. This ID number will be used on all clinical measurement forms, questionnaires, databases, and computer data entry screens. This number will be linked to subjects only in individual charts maintained in secure storage areas. Blood and urine specimens will be labeled with an institution-specific record number and sent to the Center for Advanced Laboratory Medicine (CALM) at Columbia University Medical Center for processing; results will be tracked through password-protected, access-controlled electronic medical record systems. The laboratory results will be entered by study personnel into a password protected study database containing only the study ID number as an identifier. The identification of subjects will not be included in any description or publication of the results. The protocol will be approved by the Institutional Review Board (IRB). A Data and Safety Monitoring Board (DSMB) composed of three independent cardiologists ([name], [name] and [name]) will be established and all adverse events will be promptly reported and updates will be sent to the institutional IRB. The Data Safety Monitoring Board will meet prior to the start of the trial and agree on safety measures outlined in this protocol. This will include defining a deliberative process, criteria for un-blinding or unmasking, criteria for triggering an unscheduled review and voting procedures. They will also meet both with the PI and in subsequent closed sessions to review any adverse events that occur throughout the protocol. The DSMB will meet at least one time every six months to review any events. The PI will notify the DSMB and the IRB of any serious adverse events within 24 hours of their occurrence. The DSMB will not monitor this trial for any efficacy boundary given its small nature.

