We plan to collect and store biological samples for later batch analysis. These samples will be stored in the Columbia University, [name] Lab. Subjects will be fully informed regarding the storage and potential future use of their samples during the consent process for the study.

2. List of specific tests that will be done to monitor patient safety

The following tests will be performed to ensure patients' safety:

- a) Serum chemistry (creatinine) and venous lactate on day 0, 30 and 180
- b) Vital Signs on day 30 and 180
- c) Physical Exam on day 180
- d) Adverse Event check at 30 days after endpoint of the trial (after last known dose of either placebo or study drug)

3. What adverse events/toxicities are expected?

Three safety outcomes have been designated:

- a) Worsening renal function: Decline in eGFR to $<45\text{ml}/\text{min} \cdot 1.73\text{m}^2$, day 30
- b) Venous Lactate: Rise in venous lactate level to $\geq 2.0\text{mmol/L}$ on day 30

c) Hypoglycemia defined as a fasting glucose <60mg/dL on day 30

4. What are the serious adverse events?

Serious adverse events have been designated:

- a) Death
- b) Life threatening illness
- c) Congenital Abnormality
- d) Hospitalization
- e) Venous Lactate: Rise in serum lactate $\geq 2\text{mmol/L}$, at any point
- f) Hypoglycemia: Fasting glucose <60mg/dL, at any point

GFR falling below 45ml/min is defined as a safety event because it requires dose adjustment however it is not defined as a serious adverse event.

Specific responses to anticipated possible adverse events are detailed below:

Table 2: Serious Adverse Events

Adverse Event	Action
Death	Discontinuation of study drug. DSMB will unblind the allocation and determine if the death was related to the study drug.
Life threatening illness	Discontinuation of study drug if it is either 1) unsafe to continue for medical reasons by either the treating physicians, the PI of the study, or the DSMB, or 2) if it deemed by the DSMB to be related to the study drug. The DSMB will unblind the allocation and determine if the illness is related to the study drug.

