Congenital Abnormality	Pregnancy is an exclusion criteria for this study and patients will be advised not to become pregnant during this study. However, if we detect a pregnancy that occurs during the study (there is a pregnancy test at the end of study), we will stop the study for that patient. We will mandate that we follow the patient until after birth to determine if there is a congenital abnormality. If we detect this event, the DSMB will be required to unblind the allocation (if the trial is ongoing) and determine if the congenital abnormality is related to the study drug.
Hospitalization	Discontinuation of study drug if it is either 1) unsafe to continue for medical reasons by either the treating physicians, the PI of the study, or the DSMB, or 2) if it deemed by the DSMB to be related to the study drug. The DSMB will unblind the allocation and determine if the hospitalization is related to the study drug.
Venous Lactate rises to $>2\text{mmol/L}$	Discontinue study drug, de-identification of study medication. Repeat lactate daily until normalizes. Contact primary cardiologist. Consider inpatient hospitalization.
Fasting Serum Glucose <60mg/dL	Discontinue current regimen. Administer patient oral glucose. Repeat value until normalizes. Referral to primary physician/cardiologist. Referral to ED if for referral or assessment if symptomatic and non-responsive to glucose tabs.

Renal Impairment for already enrolled patients

Glomerular Filtration Rate	Action
GFR \geq 45ml/min/1.73m ²	No action
GFR 30 - 44ml/min/1.73m ²	Reduce total dosage to 500mg twice a day. Schedule follow up basic metabolic panel in 3 months if GFR measurement occurs >3 months from scheduled end of trial. If follow up GFR is greater than 45 ml/min/1.73m ² , then patient can revert dosage to 2 grams per day. If GFR is less than 30 ml/min/1.73m ² , study drug and patient enrollment will be terminated.
GFR <30ml/min/1.73m ²	Stop Drug and patient enrollment in trial

5. Reporting of adverse events/adverse drug reactions

Adverse events (AEs) will be reported to the IRB and the DSMB. Adverse events will be reported on a weekly basis to the DSMB and serious adverse events will be reported to the IRB and DSMB within 24 hours of being detected.

6. Who will review AEs and other safety data?

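### Adverse events are said to be tracked weekly, yet no all-event query is planned between days 30 and 180, and the SAE notice clock has two different starting points

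*Combined protocol and SAP*

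**What the plan says.** On frequency and timing:

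- Safety Monitoring: "Safety will be assessed by tracking all adverse events on a weekly basis and serious adverse events within 24 hours of discovery".
- Data and Safety Monitoring Plan, item 6: "Adverse events will be reviewed on a weekly basis by three independent cardiologists". Item 5 also has adverse events going to the DSMB weekly.
- Data and Safety Monitoring Plan, item 1, on SAEs: "The PI will notify the DSMB and the IRB of any serious adverse events within 24 hours of their occurrence".
- Data and Safety Monitoring Plan, item 5, on the same notice: "serious adverse events will be reported to the IRB and DSMB within 24 hours of being detected".

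On contact with patients:

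- Table 1 has columns for days 0, 30, 180 and 210. Its adverse event row is marked at days 30, 180 and 210. Item 2 of the Data and Safety Monitoring Plan confirms the last of these: "Adverse Event check at 30 days after endpoint of the trial".
- Study Intervention and Procedures plans two office visits, at baseline and day 180, with blood work at day 30 in between.
- Clinical Events: "ADHF-events will be recorded every three months during office visits or by telephone contact". The three items listed there are unscheduled intravenous diuretic in the office, an emergency visit and an admission, all for decompensated heart failure. Table 1 has no column for this contact.
- Clinical Data Collection plans extraction from electronic medical records. It gives no frequency and no link to adverse event reporting.

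On scope, both Safety Monitoring and item 4 of the Data and Safety Monitoring Plan count a hospitalization for any cause, and a life-threatening illness, as serious.

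**The concern.** A statement that all adverse events are tracked weekly needs a procedure by which the study team learns of them. The schedule has two all-event checks during treatment, 150 days apart. The contact that falls between them is limited to heart failure events. A patient admitted on day 35 for pneumonia or a fall has had an SAE, but the next planned question that would bring it to light comes at day 180. The same holds for the nonspecific symptoms by which, according to the Study Drug paragraph under Specific study risks, lactic acidosis shows itself.

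Until then, such events reach the team only if the patient or a treating physician volunteers them, or if record extraction happens to be done in time. What is at stake is how completely and how early non-heart-failure events are captured over most of the full-dose period. Descriptive adverse event reporting would also be affected, because heart failure events are asked about at the three-monthly contact and other events are not.

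The two SAE clocks are a separate inconsistency. A clock that starts at occurrence cannot be assured when the team may first hear of an event long afterwards.

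**Working it through.** The plan gives no figure of its own to reproduce. The check is a day count from the schedule.

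**Inputs**

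- Treatment lasts 180 days, with the lower starting dose for the first two weeks (Study Intervention and Procedures).
- All-event checks during treatment are at days 30 and 180 (Table 1). Day 30 is credited as a full query because Table 1 marks it, although Study Intervention and Procedures describes only blood work on that day.
- The three-monthly contact has no stated day. Day 90 is assumed.

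**Steps**

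1. Full-dose days: 180 − 14 = 166.
2. Interval between the two on-treatment checks: 180 − 30 = 150 days.
3. Share of treatment: 150/180 = 83%. Share of full-dose days: 150/166 = 90%.
4. Literal weekly tracking would mean 180/7 = 25.7, so about 25 checks during treatment, against 2 planned.
5. Mean wait to the next planned query, for an event uniformly timed in the interval and not otherwise discovered: 150/2 = 75 days. The maximum is about 150 days.
6. If the three-monthly contact at day 90 asked about all events, the interval would split into 60 and 90 days. The mean wait would be (60 × 30 + 90 × 45)/150 = 5850/150 = 39 days, and the maximum 90.
7. Sensitivity to the assumed day, with t days from day 30 to the contact: mean wait = (t² + (150 − t)²)/(2 × 150).

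| Contact day | t | Mean wait (days) | Maximum (days) |
|---|---|---|---|
| 80 | 50 | (2500 + 10000)/300 = 41.7 | 100 |
| 90 | 60 | (3600 + 8100)/300 = 39.0 | 90 |
| 100 | 70 | (4900 + 6400)/300 = 37.7 | 80 |

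The gain hardly depends on the exact day. In every row the wait remains far longer than a week.

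**The SAE clock, side by side**

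| Place | 24 hours counted from |
|---|---|
| Safety Monitoring | discovery |
| Data and Safety Monitoring Plan, item 1 | occurrence |
| Data and Safety Monitoring Plan, item 5 | detection |
| Data and Safety Monitoring Plan, item 6 | not stated |

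Discovery and detection amount to the same thing. Occurrence does not.

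**The case against.** The case on the other side is substantial, and much of it limits what can be concluded.

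- **Weekly review is feasible.** A reader might infer that the weekly DSMB review cannot be carried out. The documents do not support that. In items 5 and 6 of the Data and Safety Monitoring Plan, weekly describes reporting and review, and both can run on whatever events are known. The mismatch is confined to the Safety Monitoring sentence about tracking, and even that can be read in the same sense. It should say so.
- **The designated safety outcomes do not rest on recall.** Item 3 names three (eGFR, venous lactate and fasting glucose), each a day-30 laboratory value, and the Statistical Approach specifies no comparison of queried adverse events between arms. To say that the safety comparison would rest on months of recall goes beyond the text.
- **Events may be found by other routes.** Record extraction covers hospitalizations and complications, and the Statistical Approach expects patients to receive regular care at the center. In-system admissions may well be found early, so it does not follow that the DSMB would see other SAEs months late. The 75 days is a wait to the next query, not a delay to detection. Still, extraction has no stated frequency or link to SAE reporting. It would miss symptoms that led to no care and may miss care given elsewhere.
- **Day 180 looks back.** Events in the interval are asked about late, not never.
- **Reporting instructions may exist.** Contact and consent pages are not in the public text, so their absence cannot be held against the plan.
- **The three-monthly contact serves a secondary endpoint.** Its focus on heart failure is endpoint collection and does not mean that other events are ignored. That explains the wording, but it leaves the interval without an all-event question.
- **Safety Monitoring puts the final visit at day 90.** That sentence concerns laboratory tests and conflicts with day 180 elsewhere. One query at day 90 would not be weekly in any case.

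**Conclusion.** The point holds as a gap between stated intent and planned procedure. No planned contact asks about all adverse events between days 30 and 180, which is 83% of treatment days and 90% of full-dose days. Non-heart-failure events in that interval, including SAEs, depend on spontaneous report, on record extraction at no stated frequency, or on recall at day 180. The mean wait of 75 days to the next query assumes uniform timing and no other route of discovery, so it describes the contact plan and does not predict actual delay. The 39 days after the change assumes a contact at day 90.

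The SAE clock is inconsistent between item 1 of the Data and Safety Monitoring Plan on one side and item 5 and Safety Monitoring on the other. The occurrence version cannot be assured with these contacts.

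Nothing here shows that DSMB oversight is unworkable or that the designated safety outcomes are compromised. It is an inexpensive improvement in safety capture, together with passages to reconcile.

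**What to change.** 1. Make the existing three-monthly visit or call an all-adverse-event contact. Ask the same short set of questions in both arms: any hospitalization or emergency visit for any cause, and the lactic acidosis symptoms already listed in the Study Drug paragraph, as well as the heart failure events.
2. Add the contact to Table 1 as its own column, with its day and a mark in the adverse event row.
3. Give the SAE notice a single starting point in Safety Monitoring and in items 1 and 5 of the Data and Safety Monitoring Plan, and state it in item 6.
4. State in Safety Monitoring that weekly means reporting and review of events discovered that week. This is needed even with the wider contact, because one query near day 90 does not deliver weekly capture.

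The cost is a few more minutes on a call already planned, some rewording, and more non-serious events to record. No dose or clinical rule changes.
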